- To assess the mean change in patient symptoms using the Numeric Rating Scale (NRS) for eye dryness at all measured time points up to Day 169.
- To assess the mean change in patient symptoms using the patient global assessment of disease activity at all measured time points up to Day 169.
- To assess the mean change in the physician global assessment at all measured time points up to Day 169.
- To assess the mean change in patient fatigue using PROMIS Fatigue assessment at all measured time points up to Day 169.
- To assess the mean change in female sexual function using the Female Sexual Function Index (FSFI) at all measured time points up to Day 169.
- To assess the mean change in patient quality of life using the SF-36 at all measured time points up to Day 169.
- To assess safety and immunogenicity of abatacept.
- To assess the pharmacokinetics of abatacept.

- Subjects should have pSS that is refractory to symptomatic or local therapy (e.g. NSAIDs)
- Subjects having an ESSDAI score of at least 5 at screening.
- Subjects being anti-SS-A/Ro positive at screening.
- Stimulated salivary flow of at least 0.1 mL/min at screening and randomization in at least 124 subjects (72%)

Key Exclusion criteria:

- Subjects who have a systemic autoimmune disease other than Sjögren's syndrome, such as RA, SLE or systemic sclerosis, that can better explain the majority of the symptoms (ie, secondary Sjögren's syndrome).
- Subjects who have another autoimmune disease or inflammatory condition that could interfere with assessment of response of pSS to therapy (eg, systemic sclerosis, inflammatory bowel disease, gout).
- Subjects with any other medical condition associated with clinical features overlapping those of pSS or that would interfere with interpretation of results, including but not limited to a history of head and neck radiation treatment, sarcoidosis, amyloidosis, graft-versus-host disease, hepatitis C, acquired immunodeficiency syndrome, and IgG4-related disease.
- Active life-threatening or organ-threatening complications of Sjögren's-syndrome (SS) disease at the time of screening based on investigator evaluation including but not restricted to the following:
 - Vasculitis with renal, digestive, cardiac, pulmonary or central nervous system (CNS) involvement characterized as severe (note: cutaneous vasculitis is allowed)
 - Active CNS or peripheral nervous system (PNS) involvement requiring high dose steroids

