- The mean change from baseline in patient fatigue using PROMIS Fatigue assessment at all measured time points up to Day 169.
- The mean change from baseline in female sexual function using the FSFI at all measured time points up to Day 169.
- The mean change from baseline in patient function using SF-36 at all measured time points up to Day 169.
- Geometric mean of trough concentration (C_{min}) of abatacept at all measured time points.
- Proportion of subjects with at least one positive immunogenicity response up to Day 169 and during 3 months follow up (for subjects who discontinue during the 6-months double-blind) and during the cumulative abatacept period and 3 months follow-up (for the cumulative abatacept population).
- Safety (proportion of subjects with adverse events, deaths, SAEs, and AEs leading to discontinuation and proportion of laboratory marked abnormalities) up to Day 169 and during the cumulative abatacept period and follow-up period.

Analyses:

Efficacy Analyses

Changes from baseline over time for ESSDAI will be analyzed using a longitudinal repeated measures analysis. The model will include the fixed categorical effects of treatment, day (is a windowed time point), baseline corticosteroid use, baseline hydroxychloroquine use, stimulated salivary flow, treatment-by-day interaction, baseline corticosteroid use-by-day interaction, baseline hydroxychloroquine use-by-day interaction, stimulated salivary flow-by-day interaction as well as, the continuous fixed covariate of baseline score and baseline score-by-day interaction. An unstructured covariance matrix will be used to represent the correlation of the repeated measures within each subject. The parameter estimations will be based on the assumption of data being missing at random (MAR) and using the method of restrictive maximum likelihood (REML). The difference in adjusted means (LSMEANS)

between abatacept and placebo at the primary time point, Day 169, and corresponding 95% CI and p-value based on the longitudinal repeated measures above will be provided.

A similar longitudinal repeated measures analysis will be provided for the key secondary endpoints, mean change from baseline in ESSPRI and mean change from baseline in the stimulated whole salivary flow and the other secondary efficacy endpoints including changes from baseline.

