8 STATISTICAL CONSIDERATIONS

8.1 Sample Size Determination

A hierarchical testing procedure will be applied for the primary endpoint (change from baseline in ESSDAI at Day 169) and the 2 key secondary endpoints (change from baseline in ESSPRI at Day 169 and change from baseline in the stimulated whole salivary flow at Day 169) to ensure the preservation of the overall type I error of 5%. The first key secondary endpoint will only be tested (at a significance level of 5%) if the test for the primary endpoint is statistically significant at a significance level of 5%. If both the test for the primary endpoint and the first key secondary endpoint are statistically significant (both at a significance level of 5%), then the second key secondary endpoint will be tested (at a significance level of 5%).

A sample size of 172 patients (86 per arm) will achieve 98% power to detect a treatment difference of 3 in changes from baseline in ESSDAI at Day 169 between the abatacept and placebo group using a two-sided t-test with a significance level (alpha) of 0.05 and assuming a common SD of 4.8. The sample size of 86 patients per arm will achieve 90% power to detect a treatment difference of 1 in change from baseline in ESSPRI at Day 169 assuming a common SD of 2. Taking into account the hierarchical procedure, a sample size of 86 patients per arm will achieve an overall power of at least 88.2% (98% multiplied by 90%) to detect both a treatment difference of 3 in mean change from baseline in ESSDAI and a difference of 1 in change from baseline in ESSPRI at Week 24 (Day 169).

The treatment differences of 3 for ESSDAI and 1 for ESSPRI correspond to the minimal clinically important improvement (MCII) for ESSDAI and ESSPRI³⁶, the key endpoints that address the major signs and symptoms of this disease. Estimates of the SD of mean change from baseline in ESSDAI derived from published results³⁷, range from 3.6 to 6.3. Estimates of the SD of mean change from baseline in ESSPRI derived from published results range from 1.7 to 2.2.³⁸

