7.1.3 Longitudinal Repeated Measures Analysis

Primary Endpoint (ESSDAI)

Changes from baseline over time for the primary endpoint, ESSDAI, will be analyzed using a longitudinal repeated measures analysis. The model will include the fixed categorical effects of treatment, day (is a windowed time point), Baseline oral corticosteroid use (yes/no), baseline hydroxychloroquine use (yes/no), baseline stimulated salivary flow ($< 0.1\text{mL}/\text{min}$, $\geq 0.1\text{mL}/\text{min}$), Japan (yes/no), treatment-by-day interaction, baseline oral corticosteroid use-by-day interaction, baseline hydroxychloroquine use-by-day interaction, baseline stimulated salivary flow-by-day interaction, Japan-by-day interaction as well as, the continuous fixed covariate of baseline ESSDAI and baseline ESSDAI -by-day interaction. An unstructured covariance matrix will be used to represent the correlation of the repeated measures within each subject. The parameter estimations will be based on the assumption of data being missing at random (MAR) and using the method of restrictive maximum likelihood (REML). The degrees of freedom will be calculated using the Kenward-Rogers method. Adjusted mean changes (LSMeans) with corresponding SE and 95% CI per treatment arm will be provided. The difference in adjusted means (LSMEANS) between abatacept and placebo at the primary time point, Day 169, and corresponding 95% CI and p-value based on this longitudinal repeated measures model will be provided. The analysis is using the modified ITT analysis population and all efficacy measurements collected up to last dose in Double-Blind Period + 42 days (and prior to start of open-label treatment).

In case of non-convergence of the preferred longitudinal model, memory space issues, or other computational issues the following back-up models are defined and will be applied sequentially.

The first back-up model that resolves the computational issues will be used.

- In the first backup model, the repeated statement will specify a spatial power covariance matrix instead of the unstructured variance-covariance matrix; and intercept and slope will be specified as random effects on a subject level. All terms and interactions will be as for the primary model.

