and baseline. The model will include the fixed categorical effects of treatment, day (is a windowed time point), Baseline oral corticosteroid use (yes/no), baseline hydroxychloroquine use (yes/no), Japan (yes/no), treatment-by-day interaction, baseline oral corticosteroid use-by-day interaction, baseline hydroxychloroquine use-by-day interaction, Japan-by-day interaction as well as, the continuous fixed covariate of baseline stimulated salivary flow and baseline stimulated salivary flow-by-day interaction. An unstructured covariance matrix will be used to represent the correlation of the repeated measures within each subject. The parameter estimations will be based on the assumption of data being missing at random (MAR) and using the method of restrictive maximum likelihood (REML). The degrees of freedom will be calculated using the Kenward-Rogers Method. Adjusted mean changes (LSMeans) with corresponding SE and 95% CI per treatment arm will be provided. The difference in adjusted means (LSMEANS) between abatacept and placebo at the primary time point, Day 169, and corresponding 95% CI and p-value based on the longitudinal repeated measures above will be provided. The analysis is using the modified ITT analysis population and all efficacy measurements collected up to last dose in Double-Blind Period + 42 days (and prior to open-label treatment).

In case of computational or non-convergence issues of the model, the following back-up models will sequentially be applied and the first back-up model that resolves the issues will be used. First, a spatial power covariance matrix will be used instead of an unstructured covariance. The second back-up model will use a spatial covariance matrix and remove the interactions with baseline stratification from the model. The third back-up model will include the spatial power covariance matrix and remove all interactions between baseline and day from the model.

Patterns of missing data for the change from baseline over time for the key secondary endpoints will be assessed using the same methods that were described for the primary endpoint in the previous section.

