8.2 Baseline Measures

For each subject, the baseline value of a parameter is defined as the last assessment of that parameter on or prior to the date/time of the first dose of the double-blind study medication.

If time of measurement of a parameter or time of first dose are missing, then the baseline value is defined as the last assessment of that parameter on or prior to the date of the first dose of the double-blind study medication.

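### The ESSDAI and stimulated-flow models adjust for one pre-treatment value although screening supplies a second: a low-cost gain in precision of uncertain size

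*Protocol*

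**What the plan says.** The protocol synopsis (Efficacy Analyses) describes a repeated measures model with "the continuous fixed covariate of baseline score and baseline score-by-day interaction". SAP 7.1.3 carries this into the primary model as "the continuous fixed covariate of baseline ESSDAI and baseline ESSDAI -by-day interaction" and into the second key secondary model as "the continuous fixed covariate of baseline stimulated salivary flow and baseline stimulated salivary flow-by-day interaction". SAP 8.2 takes as baseline the value "defined as the last assessment of that parameter on or prior to the date/time of the first dose", which is Day 1 for anyone assessed that day.

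Both measures also have a screening value:

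- **ESSDAI.** Entry is limited to "Subjects having an ESSDAI score of at least 5 at screening". SAP Appendix 2 uses the screening score again to identify relevant deviations.
- **Stimulated flow.** Protocol Table 5.1-1 schedules it at screening. Protocol 3.3.1 wants at least 124 subjects at or above 0.1 mL/min at both screening and randomization. SAP 7.1 builds the flow subgroup from CRF data.

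So both screening values are needed for work already planned. In the visible text neither enters a main, back-up or sensitivity model as a continuous covariate. The tipping-point imputation in SAP 7.1.5 conditions on baseline and Weeks 4 to 20 only. ESSPRI does not appear in the visible part of the screening table, so the point concerns ESSDAI and flow alone.

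**The concern.** A single reading of either measure is likely to be noisy. ESSDAI is scored by an assessor, and stimulated flow comes from a 2-minute gauze test. The plan itself allows for movement between the two visits: SAP 7.5.2.3 provides a Day 1 ESSDAI category below 5 although entry requires at least 5 at screening, and the low-flow subgroup is defined by screening or baseline. When one reading is noisy, a second pre-treatment reading can improve prediction of Day 169 and so reduce the residual variance of the treatment comparison.

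The case is plainest for flow. Everyone in the key secondary analysis has at least 0.1 mL/min at both visits, and that model has no flow stratum. Screening flow therefore selects the population but contributes nothing to the adjustment. At stake is some power for the first and third tests in the hierarchy.

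**Working it through.** **Inputs from the documents** (Protocol 8.1, SAP 5)

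- ESSDAI: "A sample size of 172 patients (86 per arm) will achieve 98% power to detect a treatment difference of 3 in changes from baseline", "using a two-sided t-test with a significance level (alpha) of 0.05 and assuming a common SD of 4.8". Published SDs of change range from 3.6 to 6.3.
- ESSPRI: difference 1, SD 2, 86 per arm, stated power 90%.
- Flow: difference 0.165 mL/min, SD 0.275, 62 per arm, stated power 91%.

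**Step 1: reproduce the plan's figures.** Two-sample t-test, noncentrality d / (SD × √(2/n)), 2n − 2 degrees of freedom.

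- ESSDAI: 3 / (4.8 × √(2/86)) = 4.10, power 98.3% (stated 98%). At SD 6.3: 3.12, power 87.4%.
- ESSPRI: 1 / (2 × √(2/86)) = 3.28, power 90.3% (stated 90%).
- Flow: 0.165 / (0.275 × √(2/62)) = 3.34, power 91.2% (stated 91%).
- Products: 0.98 × 0.90 = 88.2%, and × 0.91 = 80.3%, as stated.

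**Step 2: effect of a second covariate.** With complete data, a model with baseline-by-day terms behaves at Day 169 like ANCOVA. Let r = corr(Day 1, Day 169), s = corr(screening, Day 169) and c = corr(screening, Day 1). Residual variance is proportional to 1 − r² with Day 1 alone and to 1 − R² with both, where R² = (r² + s² − 2rsc) / (1 − c²). The variance ratio is (1 − R²) / (1 − r²).

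The documents give none of r, s and c, so the rows below are assumptions, with s = r except in the last row. Worked example, r = s = 0.5 and c = 0.8: R² = (0.25 + 0.25 − 0.40) / 0.36 = 0.278, ratio 0.722 / 0.75 = 0.963. The power columns take the stated SD as the residual SD after Day 1 adjustment and multiply it by √ratio.

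| r = s | c | Variance ratio | Cut | ESSDAI, SD 4.8 | ESSDAI, SD 6.3 | Flow |
|---|---|---|---|---|---|---|
| Day 1 only | – | 1 | – | 98.3% | 87.4% | 91.2% |
| 0.3 | 0.3 | 0.947 | 5.3% | 98.7% | 89.1% | 92.6% |
| 0.5 | 0.5 | 0.889 | 11.1% | 99.1% | 90.9% | 94.0% |
| 0.7 | 0.7 | 0.830 | 17.0% | 99.4% | 92.6% | 95.3% |
| 0.5 | 0.7 | 0.941 | 5.9% | 98.7% | 89.3% | 92.7% |
| 0.5 | 0.8 | 0.963 | 3.7% | 98.6% | 88.6% | 92.2% |
| 0.5 | 0.9 | 0.982 | 1.8% | 98.4% | 88.0% | 91.7% |
| 0.7 | 0.8 | 0.893 | 10.7% | 99.1% | 90.7% | 93.9% |
| s = r × c | any | 1.000 | 0% | 98.3% | 87.4% | 91.2% |

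The top cut equals about 20% more subjects (1 / 0.830 = 1.20). The last row is pure first-order decay, where screening adds nothing once Day 1 is known.

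**Step 3: the benchmark that the planned model sets.** The stated powers come from an unadjusted t-test of change. If the stated SDs are SDs of change and variances are equal across visits, Day 1 adjustment alone multiplies the SD by √((1 + r)/2). Multiplying endpoint powers as the plan does (ESSDAI × ESSPRI × flow):

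| r | Day 1 only | Adding screening, c = r |
|---|---|---|
| 0.3 | 99.9 × 98.1 × 98.4 → 96.5% | 99.9 × 98.1 × 98.8 → 96.9% |
| 0.5 | 99.7 × 96.4 × 96.9 → 93.2% | 99.9 × 96.4 × 98.2 → 94.6% |
| 0.7 | 99.3 × 94.2 × 94.9 → 88.8% | 99.8 × 94.2 × 97.6 → 91.9% |

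Setting c = r favours the proposal, and the gain is still only about 0.4 to 3 points; it falls toward zero as c rises. At ESSDAI SD 6.3 and r = 0.7 the chain would go from 92.0 × 94.2 × 94.9 → 82.3% to 95.9 × 94.2 × 97.6 → 88.2%. That is where the extra covariate would earn most.

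**The case against.** The strongest reply is that this is a preference, not a fault. The models already adjust for a continuous baseline, its by-day interaction and the stratification factors; nothing is biased or contradictory. That stands.

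A reader might infer that the 80.3% chain power shows a thin margin which screening data would lift on all three tests. The documents do not support this. The 80.3% belongs to an unadjusted t-test, and the planned model probably does better already (Step 3). ESSPRI, the endpoint with the lowest stated power, has no visible screening value to add. Nor do the documents offer a smaller flow difference at which the gain would look larger; 0.165 mL/min is the only one planned for.

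A reader might also infer that precision is certainly being lost. That too goes beyond the text. Screening and Day 1 are normally 7 to 28 days apart, while Day 169 is 24 weeks away, so c may well exceed r. Protocol 5.4.1 has the same non-protocol test results feed both the screening and Day 1 ESSDAI and strongly recommends the same assessor throughout. Both raise c and shrink the ESSDAI gain. For flow, the 0.1 mL/min cut-off at both visits restricts the range. Protocol 5.4.2 lists flow assessments from Day 1 onward and ties time of day to baseline, so comparability of the screening test is not assured.

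Finally, it is not strictly true that screening values never enter. If Day 1 is missing, screening becomes the baseline, and screening flow contributes to the two-category stratum and subgroup.

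What remains is that a continuous pre-randomization value is collected for both endpoints and is normally left out of the adjustment.

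**Conclusion.** The point holds as a low-cost efficiency gain, not as an error. The planned analysis is valid. Adding a pre-randomization covariate to a linear model leaves the target of estimation and the type I error unchanged.

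Over the assumed correlations, residual variance falls by about 0-17%, typically 2-11%. It is near zero if screening adds nothing once Day 1 is known, and toward the low end for ESSDAI. With the stated SDs read as residual SDs, power rises by at most about 1 point for ESSDAI at SD 4.8, about 5 points at SD 6.3 and about 4 points for flow. With them read as SDs of change, three-endpoint power at the planning SDs is already about 89-97% and screening adds about 0-3 points. The case therefore rests mainly on flow and on protection against an ESSDAI SD near the top of the plan's own range. Every one of these gains depends on correlations that the documents do not give.

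**What to change.** Before unblinding, in SAP 7.1.3:

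- Keep Day 1 as the baseline for change.
- Add the last screening ESSDAI before Day 1, with its by-day interaction, to the ESSDAI model. Do the same with stimulated flow in the flow model. Specifying the last value before Day 1 settles which one counts after a retest or a second screening visit.
- If the screening value is missing, use the Day 1 value.
- In the back-up sequence, drop the screening-by-day term first.
- Use the same covariate in the multiple-imputation models of SAP 7.1.5.

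The model is also described in the protocol, so its wording there should be aligned; a change to the SAP alone would leave the two documents apart.

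The cost is one term plus its by-day interaction per model: six parameters for ESSDAI (post-baseline visits on Days 29, 57, 85, 113, 141 and 169) and two for flow (Days 85 and 169). No new data, visits or subjects are needed. The downside is those few degrees of freedom, a slightly more complex model and a gain that may prove negligible.

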The binary secondary efficacy endpoints e.g., the proportion of subjects with a decrease in ESSDAI of at least 3 from baseline to Day 169 and the proportion of subjects with a decrease in the ESSPRI of at least 1 to Day 169 will be analyzed with a logistic regression including treatment, corticosteroid use, hydroxychloroquine use, stimulated salivary flow use and baseline value in the model. The odds ratio along with its 95% confidence interval will be provided. A missing responder value at Day 169 due to discontinuation or for other reasons will be imputed as a non-responder.

Safety Analyses

The proportion (%) of subjects with adverse events, deaths, SAEs, and AEs leading to discontinuation and subjects with laboratory marked abnormalities up to start of the open label period for subjects continuing in the OL or up to last dosing date +56 days for subjects discontinuing during double blind will be provided per treatment group using the as-treated population. These safety endpoints will also be summarized during the cumulative abatacept period (from the first day of abatacept treatment in the study up to 56 days after the last abatacept treatment in the study) for the cumulative abatacept population. For the cumulative abatacept population all subjects will be combined in one group.

The proportion (%) of subjects with at least one positive immunogenicity response (relative to baseline) up to Day 169 and 3 months follow up (for subjects who discontinue in the Day 169 short-term period) and during the cumulative abatacept period and 3 months follow-up (for the cumulative abatacept population) will be summarized using the immunogenicity population.

TABLE OF CONTENTS

TITLE PAGE	1
DOCUMENT HISTORY	3
SYNOPSIS.....	4
TABLE OF CONTENTS.....	12
1	16
1.1.1 Pathophysiology of Sjögren’s Syndrome	16
1.1.2 Mechanism of Action of Abatacept	17
1.2 Research Hypothesis	19
1.3 Objectives(s)	19
1.3.1 Primary Objectives	19
1.3.2 Secondary Objectives	19
1.4 Product Development Background	21
1.5 Overall Risk/Benefit Assessment	22
2 ETHICAL CONSIDERATIONS.....	22
2.1 Good Clinical Practice	22
2.2 Institutional Review Board/Independent Ethics Committee.....	23
2.3 Informed Consent.....	23
3 INVESTIGATIONAL PLAN.....	24
3.1.1 Screening Period	25
3.1.2 Double-Blind Treatment Period (Day 1 to Day 169)	26
3.1.3 Open Label Extension (Day 169 to Day 365)	26
3.1.4 Post-Treatment Follow-up Period	27

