7.1.4 Binary Secondary Endpoints

The binary secondary efficacy endpoints, e.g., the proportion of subjects with a decrease in ESSDAI of at least 3 from baseline to Day 169 and the proportion of subjects with a decrease in the ESSPRI of at least 1 to Day 169, will be analyzed with a logistic regression including treatment, oral corticosteroid use, hydroxychloroquine use, stimulated salivary flow, Japan and baseline value in the model. The odds ratio along with its 95% confidence interval will be provided. The construction of CIs for differences in response rates between treatment groups will be based on minimum risk weights to account for randomization stratification factors, unless otherwise noted.

In case there are fitting issues with the minimum risk weights model including the 4 randomization stratification variables (too small strata), the first back-up model will exclude the Japan and stimulated salivary flow randomization stratification factors. The second back-up model will exclude all randomization stratification factors. The 95% CI within each treatment arm will be based on normal approximation.

A missing responder value at Day 169 due to discontinuation or for other reasons will be imputed as a non-responder. No p-values will be provided for the binary secondary efficacy endpoints

except for the proportion of subjects with a decrease in ESSDAI of at least 5 from baseline to Day 169 and the proportion of subjects with a decrease in the ESSPRI of at least 1 to Day 169.

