7.5 Efficacy

All efficacy analyses will be provided using the modified ITT analysis population. In addition, a sensitivity analysis will be provided for the primary and key secondary endpoints using the ITT population (see [Section 6.3](#) for more details).

A hierarchical testing procedure will be applied for the primary endpoint (change from baseline in ESSDAI at Day 169) and the 2 key secondary endpoints (change from baseline in ESSPRI at Day 169 and change from baseline in the stimulated whole salivary flow at Day 169 among the subjects with stimulated whole salivary flow of at least 0.1 mL/min at both screening and baseline) to ensure the preservation of the overall type I error of 5%. The first key secondary endpoint will only be tested (at a significance level of 5%) if the test for the primary endpoint is statistically significant at a significance level of 5%. If both the test for the primary endpoint and the first key secondary endpoint are statistically significant (both at a significance level of 5%), then the second key secondary endpoint will be tested (at a significance level of 5%).

P-values will be presented for each of these 3 endpoints. However, endpoints should not be interpreted for significance if they have a rank lower than that endpoint whose null hypothesis was the first that could not be rejected. That is, the significance of endpoints should not be interpreted if they have a rank lower than that endpoint whose test was the first to be non-statistically significant (p-value > 0.05).

The proportion of subjects with a decrease in ESSDAI of at least 5 from baseline to Day 169 and the proportion of subjects with a decrease in the ESSPRI of at least 1 to Day 169 are not included in the hierarchical testing procedure, however a nominal p-value will be presented for this endpoint at Day 169

No other p-values will be presented, except for a few sensitivity analyses of the primary and key secondary endpoints (see [Section 7.1.5](#) for more details).

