7.5.2.3 Subgroup Analyses

All analyses described in this section will be performed on the modified ITT Analysis Population. All subgroups will be defined based on the data as entered on the CRF; no IWRS will be used for any subgroup analysis.

Table 7.5.2.3-1 shows the subgroups of interest for analyses of the primary efficacy endpoint of Change from Baseline at Day 169 (ESSDAI). The analysis will be using the methods described in Section 7.1.3 for each level of each subgroup, except that all stratification variables and the baseline ESSDAI day-by-day interaction will be removed from the model for this subgroup analysis. If the value of the grouping variable cannot be determined for a subject, the subject will be excluded from the corresponding subgroup analysis. Only subgroups with at least 10 patients in both treatment arms will be considered.

A forest plot showing per subgroup the estimates per treatment group and the treatment differences will be provided. The sample size for each treatment group in the subgroup will be presented along with the adjusted mean change from baseline (with 95% CI) and the treatment difference (with 95% CI).

Table 7.5.2.3-1: Subgroups of Interest

Subgroup factor	Categories
Age	< 65 Years Old
	≥ 65 Years Old
Baseline Weight	< 60kg
	60 - 100kg
	> 100kg
Gender	Male
	Female
Race	White
	Black
	Asian
	Other
Geographic Region	North America
	South America
	Asia
	Europe
	ROW
	Baseline Hydroxychloroquine use as recorded in CRF
	No
Baseline oral corticosteroid use as recorded in CRF	Yes
	No
Baseline Stimulated Salivary Flow as recorded in CRF	< 0.1mL/min
	≥ 0.1mL/min

Table 7.5.2.3-1: Subgroups of Interest

Subgroup factor	Categories
Japan as recorded in CRF	Yes
	No
ESSDAI categories at Day 1	Low < 5
	Moderate $5 \leq \text{ESSDAI} \leq 13$
	High ≥ 14

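### SAP 7.1.4 adjusts the responder odds ratio for baseline but not the response-rate difference, which can cost precision and lets the two intervals conflict

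*Protocol*

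**What the plan says.** SAP 7.1.4 gives each responder endpoint two treatment comparisons.

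- **Odds ratio.** It comes from a logistic "regression including treatment, oral corticosteroid use, hydroxychloroquine use, stimulated salivary flow, Japan and baseline value in the model".
- **Rate difference.** "The construction of CIs for differences in response rates between treatment groups will be based on minimum risk weights to account for randomization stratification factors". The baseline value is not mentioned.
- **Back-ups for the difference.** The trigger is conditional: "In case there are fitting issues with the minimum risk weights model including the 4 randomization stratification variables (too small strata"). The first back-up leaves out Japan and salivary flow. Then: "The second back-up model will exclude all randomization stratification factors. The 95% CI within each treatment arm will be based on normal approximation".
- **Missing Day 169 status** counts as non-response.
- **P-values.** Only ESSDAI ≥5 and ESSPRI ≥1 at Day 169 receive one. SAP 7.5 says these endpoints "are not included in the hierarchical testing procedure, however a nominal p-value will be presented for this endpoint at Day 169". The visible text does not say whether that p-value comes from the logistic model or from the weighted difference.

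The Protocol synopsis plans only the baseline-adjusted odds ratio: "stimulated salivary flow use and baseline value in the model. The odds ratio along with its 95% confidence interval will be provided". The mismatch therefore arises in SAP 7.1.4. Parts of the efficacy sections of both documents are redacted, and nothing is assumed about them.

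**The concern.** The same endpoint is summarised twice with different covariate sets. The SAP treats baseline score as worth adjusting for: it is in the primary and key secondary models (7.1.3) and in the logistic model. Leaving it out of the rate difference gives away precision if baseline is prognostic for response. It also creates a reporting problem: one interval may exclude no effect while the other includes it, and the plan has no rule for which governs. This matters most for the two responder endpoints with nominal p-values. If the second back-up is reached, a wholly unadjusted difference stands beside a fully adjusted odds ratio.

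**Working it through.** **1. The plan's own figures.** The documents give no rate, precision or power for any responder endpoint. The nearest figure is the primary power (SAP 5): SE = 4.8 × √(2/86) = 0.732; 3/0.732 − 1.96 = 2.14; Φ(2.14) = 98.4%, against 98% stated. It reproduces.

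**2. Size of the strata.** Four two-level factors give 2⁴ = 16 cells; 172/16 = 10.75 subjects per cell, about 5 per arm. The first back-up leaves 4 cells.

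**3. Response rates for ESSDAI ≥5.** Take SD 4.8 from the SAP and assume a placebo mean change of −2.
- Placebo: Φ((−5 + 2)/4.8) = Φ(−0.625) = 0.27.
- Abatacept, difference 3: Φ(0) = 0.50.
- Abatacept, difference 1.5: Φ(−1.5/4.8) = 0.38.
- Unadjusted SE at difference 3: √[(0.27 × 0.73 + 0.50 × 0.50)/86] = 0.072.

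**4. Gain from using baseline.** Simulation with 86 per arm and 1,500 trials per setting compared minimum risk weights over 4 cells with the difference standardised from the logistic model. Here r is the correlation of baseline with improvement. The documents do not give it.

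| r | SD ratio, standardised / weighted |
|---|---|
| 0 | 1.00 |
| 0.2 | 0.985–0.996 |
| 0.3 | 0.96–0.98 |
| 0.5 | 0.91–0.92 |
| 0.7 | 0.82–0.86 |

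Example (≥5 points, difference 3, r = 0.5): SD 0.0727 with 4 cells, 0.0739 with 16 cells, 0.0667 standardised; 0.0667/0.0727 = 0.917. Power was 93.8% for the odds ratio, 90.9% for the weighted difference and 93.9% for the standardised one.

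**5. A plausible r.** If Day 1 and Day 169 scores have equal variance and correlation ρ (an assumption), then r = √((1 − ρ)/2). So ρ = 0.5 gives r = 0.50 and ρ = 0.7 gives r = 0.39. An r near 0 needs scores that spread out over time or are almost perfectly correlated.

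**6. Range at ρ = 0.5 to 0.7.** A further simulation used 172 subjects and ESSDAI ≥5, with and without a floor at 0 and 12% non-responder imputation. Cochran–Mantel–Haenszel-type weights stood in for minimum risk weights. The standardised difference had 3 to 10% lower SD. In variance, from these rounded figures, that is 1 − 0.97² = 6% to 1 − 0.90² = 19%. Size under no effect was near 5%.

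**7. Opposite 5% conclusions in that simulation.**
- Odds ratio against weighted difference: about 1 to 8% of trials at a true difference of 3, and 9 to 16% at 1.5.
- Odds ratio against standardised difference: under 1%. This is expected, since in the planned model without treatment interactions a zero treatment coefficient gives a zero standardised difference.

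**8. Where the gain vanishes.** In a floored scenario where change was almost unrelated to baseline (correlation −0.06 to −0.12) and up to 11% of subjects were below 5 on Day 1, the SD fell by only 0.1 to 1.3%. Conflict still occurred in 1.0 to 4.5% of trials.

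**The case against.** Much of the opposing case stands.

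- A reader might infer that the rate difference is unadjusted. It is not: it accounts for the stratification factors unless the second back-up is used.
- A reader might infer that the SAP expects its strata to fail. The text sets out a contingency with prespecified back-ups.
- A reader might infer that baseline must dominate, because a subject below 5 on Day 1 cannot fall by 5 points and the SAP lists such a category. Entry requires ESSDAI ≥5 at screening, the share below 5 on Day 1 is unknown, and step 8 shows that this floor alone yields almost no gain. The gain comes from the assumed correlation.
- Non-responder imputation dilutes the benefit. With 12% missing, unrelated to baseline, the variance reduction at r = 0.5 fell from 19% to 13%.
- An odds ratio is conditional and a rate difference marginal, so they differ in size by nature. Some conflict in significance occurred even at r = 0 (1.4 to 4.1% at a true difference of 3 or 1.5).
- The plan already contains a baseline-adjusted inference, the odds ratio, with power equal to that of the proposed difference.

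These points limit the size and the stakes. They do not explain why a covariate already in the fitted model is left out of one of its two summaries, or which analysis supplies the nominal p-values.

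**Conclusion.** The point holds as a cheap improvement to SAP 7.1.4. The rate difference omits a baseline value that the odds ratio uses. If baseline is prognostic, this costs about 3 to 10% in SD for ESSDAI ≥5 under assumed Day 1 to Day 169 correlations of 0.5 to 0.7, and allows conflicting intervals at the frequencies in step 7. If baseline is unrelated to change, the loss is near nil. Variance gains of 16 to 21% can be produced under favourable assumptions, but they are the top of the range and should not be read as the expected gain. ESSPRI ≥1 was not simulated. The Protocol sentence is not at fault. The primary and key secondary conclusions are untouched, because the responder endpoints are outside the hierarchy.

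**What to change.** In SAP 7.1.4, for the full-population responder endpoints at Day 169:

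1. Obtain the rate difference by standardisation from the planned logistic model. Average every subject's predicted response with treatment set to abatacept, do the same for placebo, and subtract. Give a 95% CI by the delta method or the influence function.
2. Optionally keep the minimum-risk-weight difference as a supportive analysis.
3. State that the nominal p-values for ESSDAI ≥5 and ESSPRI ≥1 come from the treatment term of that logistic model.

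The salivary-flow subgroups, which may have as few as 10 subjects per arm, can keep the existing method and back-ups. The cost is a short SAP edit, a little programming and a departure from what is presumably the sponsor's standard weighting macro. No new data are needed.
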